### **11.3 PROCEDURE AND CONSEQUENCE FOR PATIENT WITHDRAWAL FROM STUDY**

The patients may withdraw from the study, before study completion if they decide to do so, at any time and irrespective of the reason:

- If possible, the patients are assessed using the procedure normally planned for the end-of treatment visit and post treatment safety follow-up visit.

For patients who fail to return to the site, the Investigator should make the best effort to re-contact the patient (eg, contacting patient's family or private physician, review available registries or health care database), and to determine his/her health status, including at least his/her vital status. Attempts to contact such patients must be documented in the patient's records (eg, times and dates of attempted telephone contact, receipt for sending a registered letter).

Patients who have withdrawn from the study cannot be enrolled again (treated) in the study. Their inclusion and treatment number must not be re-used.

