## 12 STUDY PROCEDURES

### 12.1 VISIT SCHEDULE

It is preferred that all study visits take place in the morning. Some visits that include only scheduled blood sampling (V3, V5, V6.1) (Week 2, Week 6, and Week 10) can be scheduled as Home Visits or clinic visits.

Patients will be considered as having completed their treatment per protocol and should complete the end of treatment visit (EOT):

- At Week 264, if sarilumab has been commercialized in their country at that time. EOT visit should be performed instead of Week 264 visit and the assessments defined in the flowchart ([Section 1.2.1](#), [Section 1.2.2](#)) should be completed.
- At any visit after Week 264 once sarilumab is commercialized in their country (applicable for patients in the countries where commercial sarilumab is not available at the time the patients completed their Week 264). Some of the assessments are NOT required at EOT for these patients; please refer to the flowchart ([Section 1.2.1](#), [Section 1.2.2](#)) for details.
  - When commercialization occurs in a given country, investigators in that country will be alerted by the Sponsor and they will inform their patients during the next scheduled study visit that their subsequent visit 12 weeks later will be the EOT visit.
- At any visit after Week 264 at the time the study is closed in 2020 in countries where commercialization has still not occurred. Some of the assessments are NOT required at EOT for these patients; please refer to the flowchart ([Section 1.2.1](#), [Section 1.2.2](#)) for details.
  - EOT visits for all patients remaining in the study at that time will occur at scheduled clinic visits over a 3-month period in order to stagger the completion of EOT visits across the study, and allow the completion of the 6-week follow up period for all patients prior to study closure. Investigators will be alerted by the Sponsor that the study closure is approaching and they will inform their patients during the next scheduled study visit that their subsequent visit 12 weeks later will be the EOT visit.
- At Week 264, for patients in the UK no matter when the sarilumab is commercially available in the country. EOT visit should be performed instead of Week 264 visit and assessments defined in the flowchart ([Section 1.2.1](#), [Section 1.2.2](#)) should be completed.

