If a patient is permanently and prematurely discontinued from treatment, all assessments planned at the end of treatment visit (EOT) should be performed. Some assessments at EOT are not required if the EOT visit occurs after Week 264, as indicated in the flowchart.

The safety follow-up visit should be performed six weeks from the end of treatment for all patients including those who discontinued before the planned end of treatment with the following exception:

- In patients who complete sarilumab treatment per protocol in countries where sarilumab is commercially available the post treatment follow-up visit may be cancelled if the patient initiates treatment with commercial sarilumab during the post treatment follow-up period. However, in this case, a telephone contact must be established with the patient to capture all AEs occurring up to the 1st administration of commercial sarilumab.

From Week 24 (Visit 8) onwards, some patients may participate in the PFS-S sub-study. No details of the sub-study assessments are described in this section. Please refer to the [Appendix R](#) for all information related to the sub-study assessments for these patients.

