### **12.1.13 Visit 50: Post Treatment safety follow-up visit**

Patients that discontinued prematurely before the planned end of treatment, or who completed their treatment per protocol should have this visit performed 6 weeks from end of treatment visit with the following exception:

- In patients who complete sarilumab treatment per protocol in countries where sarilumab is commercially available the post treatment follow-up visit may be cancelled if the patient initiates treatment with commercial sarilumab during the post treatment follow-up period. However, in this case, a telephone contact must be established with the patient to capture all AEs occurring up to the 1st administration of commercial sarilumab.

The Investigator will:

- Record vital signs including body temperature, blood pressure and HR and weight.
- Perform tuberculosis assessment. In case of suspicion of tuberculosis, refer the patient to a TB specialist for complete examination and additional work-up (see specific instructions in [Section 10.2.1](#)).
- Inquire regarding AE/SAEs and concomitant medications.
- Obtain urine for pregnancy test for female of child bearing potential.
- Obtain serum sample for PK (sarilumab) and for anti-sarilumab antibody.

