The duration of the treatment period in the study will be at least 264 weeks, or up to a maximum of 516 weeks (*except in the UK where the duration of treatment will be 264 weeks*) described in Protocol Amendment 9. However, some patients may complete this study with 260 week treatment duration per Protocol Amendment 8 before the approval of Protocol Amendment 9 in their countries. The total maximum duration of study participation for a patient may be up to 523 weeks.

- 1-week screening period if applicable
- 516-week maximum treatment period in LTS11210 (for the earliest patients enrolled in LTS11210 in 2010 if sarilumab is not commercialized by 2020)
- 6-week follow up period as required per protocol

Patients will either enter a 1-week screening period after the EOT visit (Visit 1 in LTS11210) in initial studies (for patients from EFC11072 Part A or Part B1 and ACT11575), or enrol directly into the treatment period (for patients from EFC11072 Part B2, EFC10832, SFY13370, or EFC13752, the EOT visit in the initial study corresponds to the randomization visit, Visit 1/2 in LTS11210).

At Visit 2 or Visit 1/2 (Week 0) after confirmation of eligibility, patients will be administered the first open-label dose of sarilumab at the investigational site and will be observed for 30 minutes for any medical events. At dosing time points occurring outside site visits, sarilumab can be injected by the patients, or by trained caregivers.

Patients will return for the safety follow-up visit 6 weeks after the EOT visit (V49). In case of early treatment discontinuation, patients are required to complete the EOT visit (V49) and to return for the 6-week safety follow-up visit (Visit 50) as well.

The study will be considered completed for a patient at the time he/she completes all the scheduled procedures.

An optional 12-week sub-study aiming to evaluate the usability of pre-filled syringe with safety system (PFS-S) will be conducted in some countries. Patients enrolled in LTS11210 at selected sites in those countries may participate in the PFS-S sub-study from Week 24 of the main study after providing written informed consent for the sub-study. However, patients may continue to participate in the main trial without participating in the PFS-S sub-study if they wish. Full details of the PFS-S sub-study are presented in [Appendix K](#).

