DAY	Day -7 to D-1	Wk0	Wk 2	Wk 4	Wk 6	Wk 8	Wk 10	Wk 12	Wk 24, 36, 48, 60, 72, 84, 96	Wk 108, 132, 156, 180, 204, 228...492 a	Wk120, 144, 168, 192, 216, 240, 264 a	Wk 288, 312, ..., 504 a		6 weeks after end of treatment a Post treatment follow-up
Week														
Visit no.	V 1 D-7 to D-1	V 2	HV 3 c (± 3 days)	V 4 (±3 days)	HV 5 c (±3 days)	V 6 (±3 days)	HV 6.1 c (±3 days)	V 7 (±3 days)	V 8 to V 14 (±3 days)	V15, V17, V19, V21, V23, V25...V47(±3 days)	V16, V18, V20, V22, V24, V26 V28(±3 days)	V30, V32, V34, V36, V38, ..., 48(±3 days)	V49 (±3 days)	V50(±3 days)
Anti-sarilumab antibody	X d							X	X		X	X	X	X
Serum sample to be stored for future biomarkers s	X d		X					X	X					
Expression RNA t		X d	X											

- a EOT visit and follow up visit 6 weeks later should be completed for all patients at the end of treatment (in patients who complete sarilumab treatment per protocol in countries where sarilumab is commercially available the post treatment follow-up visit may be cancelled if the patient initiates treatment with commercial sarilumab during the post treatment follow-up period; however, in this case, a telephone contact must be established with the patient to capture all AEs occurring up to the 1st administration of commercial sarilumab). EOT visit may occur when the patients complete 264 weeks of sarilumab treatment from the LTS11210, or at any visit thereafter when sarilumab is commercialized in their country, but no later than 2020 when the study will be closed. In case of permanent discontinuation of treatment, the patients will be assessed using the procedures normally planned for the EOT visit and the 6 week follow up visit 6 weeks later.
- b From Week 24, patients at limited sites in selected countries may participate in PFS-S sub-study. If the patient enters the sub-study, then the sub-study IMP will be dispensed instead of the main study IMP at the entry into sub-study and IMP compliance with sub-study IMP will be reviewed at the end of sub-study. Full details of the sub-study are provided in Appendix R
- c HV: Visit can be home visit or clinic visit to draw and collect the blood sample only for hematology and LFTs using the designated central laboratory.

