## **2.2 DISPOSITION OF PATIENTS**

This section describes patient disposition for both patient study status and the patient analysis populations for LTS11210 only, unless otherwise specified.

- All screened patients are defined as those patients who signed the informed consent.
- All enrolled patients are defined as all patients with signed informed consent who met the eligibility criteria to enter into LTS11210.
- The Safety population consists of all enrolled patients who received at least one dose of the LTS11210 study medication.

For patient study status, the total number of patients for each one of the following categories will be presented using a summary table:

- All screened patients (informed consent signed)
- Screen failure patients and reasons for screen failure (not eligible per eligible CRF page)
- Non-enrolled but treated patients
- All enrolled patients by previous studies
- Enrolled but not treated patients
- Enrolled and treated patients
- Patients who had dose reductions
- Patients who discontinued study treatment by main reason for permanent treatment discontinuation
- Status at last study contact

For all categories of patients (except for the screened and non-enrolled categories), percentages will be calculated using the total of all enrolled patients as the denominator. Reasons and time to treatment discontinuation will be supplied in tables giving numbers and percentages. This summary will be further sub-grouped by region and by prior biological use.

A patient is considered as lost to follow-up at the end of the study if he/she is not assessed at the last protocol planned visit.

All major or critical deviations potentially impacting analyses, drug dispensing irregularities and other major or critical deviations will be summarized in tables giving numbers and percentages of deviations.

The analysis populations for safety, efficacy and PK will be summarized in a table by patient counts on the enrolled patients.

- Safety population (for safety and efficacy analyses),
- PK population.

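### Does the SAP's lost-to-follow-up rule miscount completers whose Visit 50 is cancelled because they start commercial sarilumab?

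*SAP*

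**What the plan says.** SAP 2.2 (Disposition of Patients) defines loss to follow-up in one sentence: a patient is "considered as lost to follow-up at the end of the study if he/she is not assessed at the last protocol planned visit". It gives no exception and does not name the visit.

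In the flow charts of both documents the last visit is Visit 50. Protocol 12.1 requires it "for all patients including those who discontinued before the planned end of treatment with the following exception". The exception covers patients who finished treatment per protocol in a country where the drug is on the market. For them, "the post treatment follow-up visit may be cancelled if the patient initiates treatment with commercial sarilumab during the post treatment follow-up period" (Protocol 12.1.13, with the same provision in Protocol 6.2, 12.1 and the flow-chart footnotes).

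The SAP repeats the provision in footnote a of its two flow charts, including the substitute for the visit: "a telephone contact must be established with the patient to capture all AEs occurring up to the 1st administration of commercial sarilumab". The text of SAP 1.1 describes the return for follow-up without mentioning the cancellation.

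**The concern.** The SAP's definition and the protocol's permission appear to conflict. A patient who completed at least five years of treatment, moved to marketed drug and was reached by telephone was not assessed at Visit 50. On a strictly literal reading that patient is lost to follow-up.

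The same label would then cover a quite different group, described in Protocol 11.3: "For patients who fail to return to the site, the Investigator should make the best effort to re-contact the patient". One group was followed as the protocol intended and the other was not. In a long-term safety study the loss-to-follow-up figure tells readers how complete the safety observation was, so mixing the two would overstate the losses.

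The situation is not far-fetched. Several patients could finish in countries where sarilumab is already sold, and the SAP nowhere links its footnote to the disposition rule.

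**Working it through.** The plan gives no figure to reproduce, so the check is mainly a comparison of texts.

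**1. Whose plan decides which visit is last?** SAP 2.2 does not name Visit 50. It points to the last visit the protocol plans, so the protocol's conditions on that visit come with it.

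**2. What does the protocol plan for these patients?** Protocol 12.1 sets the requirement for Visit 50 and the exemption from it in the same place, and 12.1.13 repeats both. Once the visit is properly cancelled, the last visit still required is end of treatment (Visit 49), followed by a telephone call. The patient was assessed at Visit 49.

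**3. When is a patient complete?** Protocol 6.2 closes by saying that the study is complete for a patient when the procedures laid out in Section 12.1 have been done. Section 12.1 contains the exemption. SAP 1.1 carries the same completion rule, and the SAP's own schedule includes the cancellation in its footnotes. SAP 1.1 also lists the six-week follow-up as subject to what the protocol requires, so it is not wholly silent on the condition. Neither document defines loss to follow-up in these lines. Even so, a patient who has completed the study is not naturally described as lost.

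**4. Who could be affected?** Protocol 12.1 gives four ways to complete treatment per protocol:

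| Route | Drug on the market in the country? |
|---|---|
| "At Week 264, if sarilumab has been commercialized in their country at that time" | Yes, by definition |
| "At any visit after Week 264 once sarilumab is commercialized in their country" | Yes, by definition |
| Study closure in 2020 where the drug is still not marketed | No |
| UK at Week 264 | Not required |

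So 2 of 4 routes meet the country condition automatically. Completion at 260 weeks under Amendment 8 (SAP 1.1) does not require it either. This counts routes, not patients. The patient must also start commercial drug within the follow-up period, and the cancellation is optional. The documents give no number for either step.

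**5. Scale per patient.** SAP 2.2 uses all enrolled patients as the denominator.

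- SAP 1.1: 1283 + 7 + 456 + 168 + 111 = 2025, and 1/2025 = 0.049%.
- SAP 1.3: 243 + 1040 + 7 + 168 + 454 + 111 = 2023, and 1/2023 = 0.049%.

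This gives the weight of one patient. It does not estimate how many there are.

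**6. Where is the label used?** The rows listed in SAP 2.2 do not include one for loss to follow-up; the nearest is *Status at last study contact*. The populations in SAP 2.3 depend on enrolment, dosing and available samples. Person-time in SAP 2.5.1 ends at the earliest of last dose plus 60 days, last contact and death. None of these refers to the lost-to-follow-up definition.

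**The case for a change.** The strongest reply is that a reasonable reading is still not a written one. No sentence in either document says that a permitted cancellation is not a loss, the row for status at last contact is listed without categories, and two programmers could produce different counts from the same SAP. The natural reading also leaves one case unclassified: a completer whose required call was never made. The remedy would cost only a sentence and a table line.

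Part of this stands. The explicit wording is missing, and the uncalled completer is not addressed. But for the strict reading to prevail, a programmer would have to ignore the exemption in Protocol 12.1, the completion rule in SAP 1.1 and footnote a of the SAP's own flow charts. The uncalled completer missed a required procedure. Whether to call that a loss or a deviation is a choice that neither document makes, and a rule keeping such patients as lost would be a new convention. A separate table line for cancelled visits is a reporting preference.

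The example in SAP 2.1.3 that calls the follow-up visit number 29 is a leftover from older numbering: Visit 29 is now the Week 276 dispensing visit. It is a clerical slip in an illustration of the observation epochs and has no bearing on the disposition rule.

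**Conclusion.** No change to the plan follows. SAP 2.2 leaves a detail unstated, and the protocol it refers to supplies the answer: a per-protocol completer whose Visit 50 was cancelled under the commercial-sarilumab provision, and who was telephoned, is not lost to follow-up. A sentence saying so could be added at no cost, but it would not alter what the trial does or concludes.

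The possible effect is confined to how a patient is described in the disposition section. It is 0.049 percentage points per patient, for a number of patients that the documents do not give. No endpoint, event rate or analysis population is shown to change.

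This rests on two assumptions: that analysts read the protocol's visit plan together with its stated exemption, and that the mandatory telephone contact is made and recorded.

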### 2.2.1 Randomization and drug dispensing irregularities

There is no randomization procedure in LTS11210. Drug dispensing irregularities occur whenever:

- A patient is dispensed an IMP kit not allocated by the IVRS, such as, a) a patient at any time in the study is dispensed a different treatment kit than as assigned (which may or may not contain the correct assigned IMP), or b) a non-screened patient is treated with study medication reserved for enrolled patients.

Drug dispensing irregularities will be monitored throughout the study and reviewed on an ongoing basis.

All drug dispensing irregularities will be documented. If the number of irregularities is large enough to make a tabular summary useful, the irregularities will be categorized and summarized among all patients (number and percentages).

Drug dispensing irregularities to be prospectively identified include but are not limited to:

**Table 5 - Drug Allocation Irregularities**

Drug Allocation Irregularities
Kit dispensation without IVRS transaction
Erroneous kit dispensation
Kit not available
Subject switched to another site

### 2.3 ANALYSIS POPULATIONS

The primary analysis population is the safety population. All safety analyses and efficacy analyses will be performed based on the safety population.

The patients who enroll into LTS11210 study but are not treated will be reported separately, and these patients will not be in the safety population for this study.

### **2.3.1 Safety populations**

Safety population is defined as all enrolled patients who have received at least one dose of the study treatment in LTS11210.

All analyses will be performed on the safety population based on previous treatment prior to enrollment into LTS11210. This will allow for assessment of any differences between treatment groups based on previous treatment.

### **2.3.2 Efficacy population**

The efficacy analysis population is the same as safety population.

Efficacy analyses will be performed on the safety population based on previous treatment prior to enrollment into LTS11210. This will allow for assessment of the efficacy improvement if it is related to the different original treatments. Note that X-ray data will be collected for patients from EFC11072 Part B Cohort 2 and Cohort 1 selected dose arms only.

### **2.3.3 Pharmacokinetics and immunogenicity population**

The PK population will consist of all patients in the safety population with at least one post-dose non-missing plasma concentration value. The ADA population will consist of all patients in the safety population with at least one post-dose, evaluable ADA sample. Patients will be analyzed according to the treatment actually received.

## **2.4 STATISTICAL METHODS**

### **2.4.1 Demographics and baseline characteristics**

Only patients enrolled and treated in LTS11210 will be summarized on demographic and baseline characteristic data.

Continuous data will be summarized using number of available data, mean, SD, median, minimum, and maximum. Categorical and ordinal data will be summarized using number and percentage of patients.

Parameters described in [Section 2.1.1](#) will be summarized based on the safety population using descriptive statistics.

Medical and surgical history will be summarized on the safety population by system organ class (SOC) and preferred term (PT) sorted by internationally agreed order of SOC and by the decreasing frequency of PT within SOC.

No specific description of the safety/efficacy parameters will be provided at baseline. If relevant, the baseline values will be described along with each safety/efficacy analysis.

## 2.4.2 Prior or concomitant medications

Prior medications are those the patients used prior to first IMP intake in LTS11210. The data before enrollment were collected and reported in the previous studies. However the data from enrollment up to the time of first IMP intake will be reported in LTS11210 database.

Prior and concomitant medications in LTS11210 will be presented based on the enrolled population.

Medications will be summarized by treatment received according to the WHO-DD dictionary, considering the first digit of the ATC class (anatomic category) and the first three digits of the ATC class (therapeutic category). All ATC codes corresponding to a medication will be summarized. Patients will be counted once in each ATC categories (anatomic or therapeutic) linked to the medication, therefore, patients may be counted several times for the same medication. In addition, the summaries for concomitant DMARDs (MTX, non-MTX DMARDs), folic acid, NSAIDs, corticosteroids, and lipid modifying agents will also be provided.

The tables for concomitant medications will be sorted by decreasing frequency of anatomic category followed by all other therapeutic classes. In case of equal frequency regarding anatomic categories (respectively therapeutic categories), alphabetical order will be used.

